7 ASSESSMENT OF SAFETY

7.1 Adverse Events

An Adverse Event (AE) is broadly defined as any untoward medical occurrence in a patient or clinical investigation occurring after the patient has signed the study consent form. The AE does not necessarily have a causal relationship with the study treatment or study procedures. Consequently, AEs include adverse drug reactions, significant abnormal laboratory values and intercurrent diseases.

AEs are expected when their nature, severity or outcome are consistent with the latest version of the Investigator's Brochure for XIAFLEX®. At each patient visit, from the date the patient provides written informed consent until the end of the study, each patient will be asked non-leading questions regarding their well-being since the last visit. Any unintended and unfavourable sign (e.g. a clinically significant abnormal laboratory finding), symptom or disease described by the patient or noted by the site staff will be recorded as an AE in the source documents, on the study CRF and followed up with more specific questions or actions as required.

If a change in the patient's health status was noted prior to drug administration, it will be recorded in the patient's source documents and in the medical, surgical or physical screening CRF pages. Only medically qualified personnel must assess AEs. For the purpose of data collection, all untoward events that occur after informed consent

through 12 months of the study period are to be recorded on the CRF by the study site. This requirement includes AEs recorded from unscheduled visits as well as scheduled visits.

7.2 Reporting of Adverse Events

All AEs must be recorded on the study CRF and described using appropriate medical terminology. If a sign or symptom is one component of a diagnosis or syndrome, then only the diagnosis or syndrome should be recorded on the AE page of the CRF. Each event is to be evaluated for duration, severity, relationship to the investigational product/procedure and any action taken.

A pre-existing condition should not be reported as an AE at baseline but must be reported in the appropriate section of the baseline CRF. Medical conditions/diseases present at baseline before the study procedure are to be considered as an AE only in cases where they worsen after starting the study.

7.3 Serious Adverse Events

We define serious adverse events (SAEs) as any untoward medical occurrence that results in death, is life threatening, requires inpatient hospitalization or prolongation of existing hospitalization or events that are believed with a reasonable level of certainty to be associated with participation in the trial . For such events research personnel will complete an SAE CRF and immediately fax or email it to the PI's office, who will then inform the necessary authorities.

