
The two previous RCTs (CORD I and CORD II) have greatly influenced the adoption of collagenase, which now stands as a legitimate contender to palmar fasciectomy for DD.

The main methodological weakness of the CORD I and CORD II trials is that the comparative intervention was placebo. Many trial methodologists would be concerned with using a placebo when existing surgical techniques exist such as the commonly performed palmar fasciectomy. We believe that presently, we are uncertain if collagenase, a non-surgical treatment is superior to palmar fasciectomy, a surgical treatment. An RCT is warranted for a head-to-head comparison. Zhou et al. directly compared CI to LPF in a propensity score matched study and found that CI was not significantly different from LPF in reducing metacarpophalangeal joint contractures. CI was also inferior to LPF in correcting proximal interphalangeal joint contractures. On the positive side, CI provided a more rapid recovery of hand function than LPF and was associated with fewer serious adverse events [12]. However, their study evaluated only short-term clinical results at 12 weeks after surgery and included a minimal number of recurrent cases in their sample. They also acknowledge the limitation of propensity matching in terms of confounding and that a well-designed randomized trial would help eliminate some confounding factors. Their overall conclusion stated that long-term effectiveness trials are still needed in head-to-head comparison studies. Based on the available evidence we believe that there presently exists a state of equipoise, which is a precondition for an RCT comparing the effectiveness of these two approaches.

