7.4 Reporting of Serious Adverse Events

Any SAE, regardless of causal relationship, must be reported to the principal investigator's office immediately (i.e. within 24 hours of knowledge of the event) on the SAE CRF and should be accompanied by any relevant documents. All SAEs that have not resolved upon discontinuation of the patient's participation in the study must be followed until either the event resolves, stabilizes, or returns to baseline. Investigators are responsible for reporting SAEs to their local ethics committee according to local regulations.

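### Section 7.3 makes any clearly trial-related event serious, however minor, and omits lasting disability, so the SAE category mixes seriousness with relatedness

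*Combined protocol and SAP*

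**What the plan says.** All the relevant text is in section 7 of the combined protocol and SAP.

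- **7.3** first defines an SAE by outcome, as an occurrence that "results in death, is life threatening, requires inpatient hospitalization or prolongation of existing hospitalization". The sentence then continues, after an or, with a further alternative: "events that are believed with a reasonable level of certainty to be associated with participation in the trial". Each such event calls for an SAE form sent at once to the principal investigator's office, which informs the authorities.
- **7.4** adds the 24-hour limit and applies it whatever the cause: "Any SAE, regardless of causal relationship, must be reported to the principal investigator's office immediately". It also requires that unresolved SAEs be followed after the patient leaves the study, and that sites report SAEs to their ethics committees.
- **7.2** covers all adverse events: "Each event is to be evaluated for duration, severity, relationship to the investigational product/procedure and any action taken". Severity and relatedness are thus recorded for every event. Seriousness is not in that list.

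Neither section 7 nor any other section gives a narrower SAE definition or lists lasting disability or incapacity as a criterion. Section 3.3 names no safety outcome, and section 8 specifies no AE or SAE analysis.

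**The concern.** Seriousness and relatedness are different attributes of an event. Seriousness describes what happened to the patient; relatedness is a judgement about the cause. Section 7.3 lets the second stand in for the first.

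Two errors follow, in opposite directions. Minor reactions that plainly come from the injection or the operation enter the SAE category and trigger expedited reporting. Some events that matter most in a trial of hand function can stay out of it, because permanent loss of function is not listed and need not involve a hospital stay.

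At stake are the usefulness of the expedited reports and the meaning of any SAE table that is published. A reader of such a table would take the count to be a count of serious harm. Sites may also differ: one that applies 7.3 literally and one that applies only the outcome criteria would report different events under the same name.

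**Working it through.** The documents state no SAE rate or count to reproduce. The check is to apply 7.3 as written, and as it would be after the fix, to five kinds of event.

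| Event | Outcome criteria in 7.3 met? | Relatedness limb met? | Class as written | Class if defined by outcome, with disability added |
|---|---|---|---|---|
| A. Minor, clearly related, no admission | No | Yes | SAE | AE |
| B. Minor, not related, no admission | No | No | AE | AE |
| C. Disabling, clearly related, no admission | No | Yes | SAE | SAE |
| D. Disabling, cause uncertain, no admission | No | No | AE | SAE |
| E. Admission, not related | Yes | No | SAE | SAE |

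**Rows A and D are misclassified.** A and B can be equally mild, and differ only in the judgement about cause. C and D can be equally disabling, and differ only in the same judgement.

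**Row A will occur.** Section 1.1 says that collagenase injections have several known adverse effects, mostly well tolerated. Section 4.5.2 expects a visible scar after fasciectomy, so minor procedure-related events are plausible in that arm too.

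**Row D is possible.** Section 5.1 places the injection in a clinic or minor procedure room, and section 5.2 sends fasciectomy patients home the same day. A lasting loss of function need not lead to admission, so the hospitalization criterion cannot be relied on to catch it.

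**Row C shows why deleting the limb is not enough.** Section 1.1 calls tendon rupture the most severe collagenase complication. Without admission, a related rupture is an SAE today only through the relatedness limb. If that limb is removed and nothing is added, the rupture falls out of the category.

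**Reading the or in 7.3 as an and does not help.** Row E would then cease to be an SAE, and the statement in 7.4 that SAEs are reported whatever their cause would have nothing to apply to.

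**Size.** The effect depends on the rate of minor related events and on the rate of disabling events of uncertain cause without admission. The documents give neither. The one complication rate they give, about 0.5% for tendon rupture, does not supply them. No count is therefore offered.

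**The case against.** The strongest reply is that this is loose wording with little consequence. Much of that reply is right.

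- **Comparison by arm.** A reader might infer that the trial's SAE comparison between arms would measure relatedness in place of seriousness. The documents do not support this. No such comparison is planned, the outcome criteria remain, so the count is a mixture, and related events can occur in both arms. No distortion between arms is shown.
- **Conflict with 7.2 and 7.4.** A reader might say that 7.3 contradicts both. It does not. A site can rate relatedness for every event under 7.2, use that rating in the last limb of 7.3, and report everything that meets 7.3 under 7.4. The arrangement is redundant and awkward, but it can be followed.
- **Expectedness.** Section 7.1 says "AEs are expected when their nature, severity or outcome are consistent with the latest version" of the XIAFLEX brochure. It is tempting to conclude that every surgical complication is unexpected by rule. The sentence does not say that an event is expected only then, and no step in 7.2 to 7.4 uses expectedness.
- **Comparability with earlier evidence.** Section 1.1 reports that in a propensity-matched study collagenase "was associated with fewer serious adverse events". That study's SAE definition is not in the documents, so whether this trial's counts could be set beside it cannot be decided here.
- **Nothing is lost.** Every untoward event through 12 months goes on the case report form with its severity (7.1, 7.2), a disabling event judged related is already an SAE, and hand function is measured at each study visit. This stands: an event in row D is recorded, and what it loses is SAE status, with the expedited report and the follow-up that go with it.

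None of this changes how rows A and D are classified. Severity grading lets an analyst separate events afterwards, but it does not alter what must be reported within 24 hours or what an SAE table counts.

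**Conclusion.** The definition is wrong as written, within limits. Followed literally, 7.3 turns any clearly related event into an SAE and leaves out a disabling event of uncertain cause that does not lead to admission. The SAE category is then a mixture of seriousness and relatedness.

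The effect falls on expedited reporting and on any SAE table that is published. It does not touch the primary MHQ comparison, and it does not mean that events go unrecorded. Its size is not known, because the documents give no rate for either kind of misclassified event.

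The conclusion rests on the literal wording and on the absence of a narrower definition anywhere else in the document. If the relatedness limb was meant to cover only important related events, the text does not say so, and a site has no means of knowing it.

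**What to change.** In 7.3, delete the relatedness limb and define seriousness by outcome only. Keep the present outcome criteria and add two: persistent or significant disability or incapacity, and other medically important events. The additions must be made together with the deletion; otherwise a related tendon rupture without admission would lose SAE status.

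Keep relatedness as the separate item that 7.2 already requires for every event. The rule in 7.4 that SAEs are reported whatever their cause then applies cleanly.

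The cost is wording in the protocol and on the SAE form, with the ethics board review that section 9.2 requires for any amendment. No new data collection is needed, and minor related events would no longer need expedited reports.

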7.4 Reporting of Serious Adverse Events

Any SAE, regardless of causal relationship, must be reported to the principal investigator's office immediately (i.e. within 24 hours of knowledge of the event) on the SAE CRF and should be accompanied by any relevant documents. All SAEs that have not resolved upon discontinuation of the patient's participation in the study must be followed until either the event resolves, stabilizes, or returns to baseline. Investigators are responsible for reporting SAEs to their local ethics committee according to local regulations.

8 STATISTICAL CONSIDERATIONS

8.1 General

Analysis of baseline characteristics will be performed using descriptive statistics reported by group as mean (standard deviation [SD]) or median (first quartile, third

quartile) for continuous variables and count (percent) for categorical variables. All analyses of primary and secondary outcomes will follow the intention-to-treat principles. We will use multiple imputation to handle missing data [25]. The results for comparisons between groups will be presented as mean difference (for continuous outcomes) and relative risk (for binary outcomes), corresponding 95% confidence intervals and associated p-values. P-values will be reported to four decimal places with p-values less than 0.001 reported as $p < 0.001$. All analyses will be performed using SAS software version 9.4 (Cary, NC, USA).

8.2 Sample Size Determination

The sample size will be based on the 12 month post-randomization MHQ score adjusted for baseline MHQ score. According to the paper by London, Stepan and Calfee [26] the MCID for the total MHQ score from an ROC analysis of patients from a population with multiple hand and forearm diagnoses is 8.7. The MCID for the total MHQ score falls between 8-13 points (depending on the method used to obtain an MCID) with a mean equal to 10.8. If we adopt an MCID of 8.7 it will be in the lower end of the range of estimates which will require a larger sample size than if the MCID were larger. For an estimate of the SD of the total MHQ score for patients with DD we obtain a value of 15.0 from the one week pre-operative assessment and 16.0 for the 12 month post-operative assessment based on the papers by Thoma et al [27,28]. The midpoint of these two estimates is 15.5.

If we use $\alpha=0.05$, $\beta = 0.80$, $MCID=8.7$ and $SD=15.5$ for the sample size calculation, assuming a correlation value of 0.0 between baseline and 12-month post-randomization MHQ scores, based on the method outlined in Borm et al[29] the required total sample is 102 patients, or 51 per group. If we account for a 20% loss to follow-up rate the required sample increases to 128 (64 per group). These calculations assume that the relationship between the baseline and 12 month post-randomization MHQ scores is linear and that the slopes of the best fit lines of the two groups are parallel.

8.3 Clinical Effectiveness Analysis

The clinical effectiveness of the collagenase will be assessed using the following HRQL instruments: MHQ, HUI3, URAM and SDSS (see section 6.4 for details). Objective measures of ROM will also be conducted and used to evaluate improvement and recurrence rates.

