3.3 Secondary Outcome Measures

Secondary outcomes include:

- (a) HRQL measured with the Health Utility Index Mark 3 (HUI3), a generic multi-attribute health-status classification instrument [15].
- (b) HRQL measured with the Unité Rhumatologique des Affections de la Main (URAM), a disease-specific HRQL measure developed for Dupuytren's contracture [16].
- (c) HRQL measured with the Southampton Dupuytren's Scoring Scheme (SDSS), a disease-specific scoring system developed for Dupuytren's contracture [17].
- (d) Quality Adjusted Life Years (QALY) measured with the HUI3. QALY is an important component of Cost-Utility Analysis (CUA), a variant of Cost-Effectiveness Analysis

(CEA); therefore, we will be able to calculate incremental cost per QALY gained between the two treatments. Utility scores of HRQL derived from responses to the HUI3 questionnaire have the required measurement properties for calculating QALYs[18].

- (e) Self-reported healthcare utilization (e.g. visits to hand surgeons, family physician, parking costs, etc.) and productivity loss (e.g. time lost from work and leisure activities by patient and caregiver).
- (f) Range of motion (ROM) of hand joints measured with goniometry
- (g) Recurrence rates defined as an increase in joint contracture in any treated joint of at least 20 degrees at one year post-treatment.
- (h) Necessary Dupuytren's Disease treatments applied to the previously affected digit(s) (the digit(s) treated in the EXTEND trial) up to 4 years following their original (EXTEND trial) treatment.

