4.1 Inclusion Criteria

1. 18 years of age or older
2. Dupuytren's contracture of the metacarpophalangeal (MCP) joint or of the proximal interphalangeal (PIP) joint with a fixed flexion contracture of 20° or greater in at least 1 finger (not the thumb)
3. Demonstrated inability to simultaneously place the affected finger and palm flat on a table
4. Able to understand and communicate in English

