4.5 Treatment Assignment Procedures

4.5.1 *Randomization Procedures*

Eligible, consenting patients will be randomly allocated (1:1) to receive either CI or LPF using block randomization to ensure equal group sizes. Allocation will be determined in advance using a computer-based random number generator and stratified by primary joint type (MCP or PIP). We will use central randomization via a web-based system generated by the Biostatistics Unit at St Joseph's Healthcare—Hamilton. The randomization will be blocked within strata using randomly permuted blocks of various sizes. Approximately 2-3 months prior to their procedure, eligible, consenting patients will be randomized to one of the 2 treatments.

4.5.2 *Masking Procedures*

Blinding of patient and surgeon will not be possible. No or very minor scar is expected from collagenase injections. For palmar fasciectomy however, a noticeable scar is expected. As such, the patients will know which procedure they received. Outcome assessors will be hand occupational therapists or physiotherapists who will perform the goniometric measurements. Although they cannot be blinded for the same reason, they nevertheless work independent of the surgeon and therefore the risk of bias in the measurements will be mitigated. The statistician for the study however, can be blinded as he will be unaware of group allocation (Study A vs Study B).

As the palmar fasciectomy can be performed some weeks later there is a risk of cross-over but this can be avoided by obtaining the consent for palmar fasciectomy in the same clinic visit as the randomization.

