5 STUDY INTERVENTIONS

5.1 Collagenase Injection (CI) Group

This procedure will be performed either in a minor procedure room or the hand clinic as per surgeon's routine practice. Collagenase will be administered with or without local anesthesia. As this is a pragmatic study we may inject more than one digit at a time just as we operate on more than one digit at a time. A recently published study by Gaston et al confirmed that two concurrent injections of CI to 2 affected joints in the same hand are generally well tolerated and the frequency of most AEs is similar to those reported in studies that use single sequential injections [19].

The patient's affected hand will be prepped with antiseptic solution. Using a hubless syringe with 0.01 mL graduations and a permanently fixed 26- or 27-gauge $\frac{1}{2}$ inch needle the required amount of reconstituted collagenase clostridium histolyticum will be withdrawn as follows: a) Cord affecting an MP joint, withdraw 0.25 mL of the reconstituted solution; b) Cord affecting a PIP joint: withdraw 0.20 mL of the reconstituted solution per published guidelines.

While applying tension to the cord in the hand to be treated, the needle will be placed into the cord while carefully ensuring that the tip stays within the cord and does not pass through the cord. After confirming the needle is placed correctly in the cord,

approximately one-third of the dose is injected. The needle tip is then withdrawn from the cord and repositioned in a slightly more distal location to the initial injection in the cord (approximately 2 to 3 mm) and another one-third of the dose is injected. Again, the needle tip is withdrawn from the cord and repositioned proximal to the initial injection (approximately 2 to 3 mm) and the final portion of the dose injected into the cord. When injecting a cord affecting the PIP joint of the fifth finger, the needle insertion should not be more than 2 to 3 mm in depth and injecting more than 4 mm distal to the palmar digital crease should be avoided.

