5.4 Procedures for Training of Clinicians on the Interventions

As CI is the “novel” intervention in this RCT, we need to consider the learning curve. Participating surgeons will be expected to review the detailed description of the technique, by viewing the provided learning video (http://www.xiaflexrems.com/video/dupuytren/Xiaflex_REMS.html) and have performed at least 10 CI injections with successful correction of the extension deficit (less than 5°) without serious complication before they begin the enrollment in the study.

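### Range of motion has no stated unit of analysis although several digits per patient may be treated; specify one value per patient, adjusted for baseline and joint type

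*Combined protocol and SAP*

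**What the plan says.** - **Outcome.** Section 3.3(f) lists "Range of motion (ROM) of hand joints measured with goniometry". It names no joint, no summary over joints and no visit.
- **Several digits.** Eligibility in 4.1 asks for a "fixed flexion contracture of 20° or greater in at least 1 finger (not the thumb"), and 5.1 states that "we may inject more than one digit at a time just as we operate on more than one digit at a time". The number of treated joints per patient is not given.
- **Analysis.** Section 8.1 has one rule for all outcomes: "The results for comparisons between groups will be presented as mean difference (for continuous outcomes) and relative risk (for binary outcomes"), with 95% confidence intervals and p-values. Adjustment for baseline is stated for the MHQ (2.1, 8.2) and for nothing else. No mixed or clustered method is named.
- **Use of ROM.** Section 8.3 states: "Objective measures of ROM will also be conducted and used to evaluate improvement and recurrence rates". Recurrence is specified in 3.3(g): "Recurrence rates defined as an increase in joint contracture in any treated joint of at least 20 degrees at one year post-treatment". Improvement has no definition and is not in the list of secondary outcomes.
- **Primary joint.** Randomization in 4.5.1 is "stratified by primary joint type (MCP or PIP"), and the first exclusion criterion in 4.2 also refers to a primary joint. Neither section says how that joint is chosen or ties it to the ROM analysis.
- **Visits.** ROM is measured at baseline and at 1, 3, 6 and 12 months (6.2, 6.3, Appendix).

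**The concern.** Patients are randomized, so all treated joints of one patient are in the same arm and their measurements are likely to be correlated. If each joint entered the comparison as a separate observation, the mean difference in 8.1 would have too small a standard error, and patients with more treated joints would carry more weight.

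The choice of joints may also move the estimate. Section 1.1 describes a propensity-matched study in which collagenase did not differ significantly from fasciectomy at the MCP joint but was inferior at the PIP joint. The mix of joints analysed therefore matters to the ROM result as well as to its interval.

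Even with one value per patient, a comparison without baseline ROM and joint type leaves out two variables that the trial already records.

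**Working it through.** **1. The plan's own figure.** No figure is given for ROM. The only sample size is for the MHQ (8.2): difference 8.7, SD 15.5, alpha 0.05 (taken as two-sided), power 0.80 (printed as beta), baseline correlation 0.0.

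- Normal approximation: n per arm = 2 × [15.5 × (1.96 + 0.84) / 8.7]² = 49.8. The exact t-test gives 50.8, so 51 per arm and 102 in total.
- Loss to follow-up: 102 / (1 − 0.20) = 127.5, so 128.

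The figure reproduces, and nothing below changes it.

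**2. What pooling joints would do.** Let m be the joints per patient and ICC the within-patient correlation. Neither is in the documents, so both are assumed. The treatment is constant within a patient, so

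- design effect DE = 1 + (m − 1) × ICC
- true coverage of a naive 95% interval = 2Φ(1.96 / √DE) − 1
- naive width relative to correct width = 1 / √DE

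| m | ICC | DE | Relative width | Coverage | Type I error |
|---|---|---|---|---|---|
| 1.5 | 0.3 | 1.15 | 0.93 | 93.2% | 6.8% |
| 1.5 | 0.7 | 1.35 | 0.86 | 90.8% | 9.2% |
| 2 | 0.3 | 1.30 | 0.88 | 91.4% | 8.6% |
| 2 | 0.7 | 1.70 | 0.77 | 86.7% | 13.3% |

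Unequal numbers of joints: if half the patients had one joint and half had two, m is replaced by Σm²/Σm = 2.5/1.5 = 1.67. DE is then 1.20 to 1.47 and coverage 92.6% to 89.4% for ICC 0.3 to 0.7.

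Wider assumptions (1.5 to 3 joints, ICC 0.2 to 0.7) give coverage from 93.8% down to 79.4%.

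**3. One value per patient.** With m = 1, DE = 1 and coverage stays at 95%. This holds for the primary joint and equally for a patient-level mean or sum.

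**4. What baseline adjustment adds.** The covariance-analysis formula that 8.2 already relies on multiplies the variance by 1 − ρ², where ρ is the correlation between baseline and 12-month values. The documents give no ρ for ROM. Assuming 0.3 to 0.7, the factor is 1 − 0.09 = 0.91 to 1 − 0.49 = 0.51, so the interval is √0.91 = 0.95 to √0.51 = 0.71 times as wide as for unadjusted 12-month values. If ρ is near zero, almost nothing is gained and almost nothing lost. A raw change score has factor 2(1 − ρ), which exceeds 1 − ρ² by (1 − ρ)² and so is never more precise.

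**5. Improvement.** The wording in 8.3 allows continuous change or a responder rate. For the second reading only, an illustrative simulation was run with no treatment effect and 51 patients per arm. Taking the best of three candidate responder definitions raised the false-positive rate from about 5% to about 13%; three independent tests would give 1 − 0.95³ = 14.3%. The distributions and definitions were assumed.

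**The case against.** A reader might infer that the plan analyses joints as independent observations. The documents do not support that. Section 3.3(f) describes what is measured, and 8.1 describes how results are presented. A primary-joint value, a patient mean or a mixed-model estimate could all be reported as a mean difference, and the unit randomized is the patient. This objection stands: the defect is an unstated unit, and the coverage figures apply only if joints are pooled.

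A reader might also infer that an improvement rate will be defined once results are known. Section 3.3 lists no responder outcome, and improvement may simply mean continuous change. Section 4.5.2 adds that the statistician can be blinded to group. That is a partial safeguard, since patients, surgeons and goniometry assessors are not blinded. What remains is a request to say which reading applies.

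Nor do the documents supply a ready threshold. The phrase "successful correction of the extension deficit (less than 5" degrees) in 5.4 is an experience requirement for surgeons' earlier collagenase injections, not a trial endpoint.

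Two further limits are fair. Recurrence, with its rule of any treated joint, reads as a patient-level event, so the clustering concern does not clearly extend to it. And confining ROM to the primary joint would put it on a different set of joints from recurrence and set aside part of the multi-digit design. That is a reason to keep the other joints in a supportive analysis.

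**Conclusion.** The plan leaves the ROM unit of analysis and comparison visit open, and provides neither a method for correlated joints nor baseline adjustment for this outcome. If joints were pooled as independent, a nominal 95% interval would cover roughly 87% to 93%, given an assumed 1.5 to 2 joints per patient and ICC 0.3 to 0.7. With one value per patient the loss is nil. The documents do not settle which will happen, so these figures describe a risk and not an error in the plan as written.

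The firmest part of the point is the remedy: a patient-level comparison adjusted for baseline ROM and joint type protects the interval and should gain precision whenever ROM at baseline and 12 months are correlated. The effect is confined to a secondary outcome.

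**What to change.** In 8.3, with a matching clarification in 3.3(f):

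1. Compare 12-month ROM between arms at patient level, with one value per patient (for example the primary joint), in a linear model adjusted for baseline ROM and the MCP/PIP stratification factor. Report the adjusted mean difference with its 95% CI.
2. If the primary joint is used, state how it is identified and record it at randomization.
3. Analyse any data with several joints per patient in a mixed model with a patient random effect, or with cluster-robust standard errors.
4. State before group results are seen whether improvement is continuous change or a responder rate. If it is a responder rate, the investigators choose the threshold and visit and record them then.

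The cost is wording. ROM is already scheduled at baseline and all follow-up visits, and joint type is already a stratification factor. The trade-off is that, if the primary joint is chosen, the other joints become supportive. One caution: 6.1 places the baseline assessment about a week before the procedure and randomization 2 to 3 months before it. Baseline ROM is therefore a pre-treatment covariate but not a pre-randomization one, and the text should say so.
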